6.3.1 Data Collection and Follow-up for Withdrawn Subjects

Subjects who withdraw consent to participate will have one final visit to collect helmet (if applicable), diaries, and questionnaires, and to follow up regarding adverse events.

6.4 Early Termination Visits

Subjects who withdraw consent to participate will have one final visit to collect helmet (if applicable), diaries, and questionnaires, and to follow up regarding adverse events.

7 Study Evaluations and Measurements

7.1 Demographics/Medical History

Study staff will collect baseline demographics and medical history at screening visit. A medical history will be reviewed and recorded at the Screening visit. Epilepsy history including etiology, seizure type(s), description, duration, and resulting falls will be documented.

7.2 Physical and Neurological Exam

The principal investigator or designated sub-investigator (MD or NP) will perform a baseline physical and neurological exam and document findings in the subject's file. Follow up physical and neurological exams will be performed at visits 2 and 3. The systems to be reviewed will be left to the Investigator's judgment.

7.3 Pregnancy Testing

A urine pregnancy test will be performed for female subjects of childbearing potential. Subsequent urine pregnancy tests may be administered at the investigator's discretion if there is reason to believe the subject may be pregnant. Pregnant subjects will be removed from the study.

7.4 Subject Training

Subjects in the helmet group will be trained on proper use of the Hövding Inflatable Helmet and will be provided with an information packet. Subjects or their caregivers will also be trained on the completion of seizure calendars and questionnaires.

7.5 Seizure Calendar

At the first screening visit, all subjects will be given copies of a seizure calendar. On a daily basis, the subject or theior caregiver is to complete this calendar, which will capture self-reported (or observed by caregiver) seizures and helmet wearing, as well as seizure-free or helmet-free days. At subsequent visits, this seizure calendar will be reviewed and collected. A new calendar will be given at visit 2.

7.6 Seizure Questionnaire

At visits 1 and 2, all subjects will be given copies of the seizure questionnaire to be filled out after the subject has a seizure. This questionnaire will capture information such as whether or not the subject was wearing the helmet, whether or not the helmet deployed, the position the subject was in during the seizure, what happened during the seizure, and whether the subject was injured or needed medical attention.

7.7 Helmet Deployment Questionnaire

At visits 1 and 2, subjects in the helmet group will be given copies of the helmet deployment questionnaire to be filled out after the helmet deploys (either during a seizure or otherwise). This questionnaire will capture information such as whether a seizure caused the helmet to deploy, what the subject was doing at the time, whether any injuries were obtained, and whether any medical care was needed or obtained.

7.8 Rivermead Post-Concussive Scale

At visits 1 and 2, subjects able to complete the scale will be given copies of the Rivermead Post-Concussive Scale to be filled out at baseline and 48 hours after a seizure if the subject sustains a head injury during a seizure or if the helmet deploys during a seizure. This questionnaire will capture information regarding cognitive, somatic, and emotional symptoms associated with post-concussion syndrome.

7.9 Injury-Related Medical Record Collection

If subjects seek medical care for injuries during the trial, the study staff will collect any information available, including medical records. Medical records from the University of Pennsylvania will be collected via the electronic medical record. The study staff will make all efforts to obtain related records from all other sites not affiliated with the University of Pennsylvania with the subject's permission.

7.10 Monthly Contact

Study staff will establish contact with subjects monthly via phone or email to ask about seizure frequency, falls, and time spent wearing the helmet. Staff will document the communication in subject files.

8 Statistical Plan

8.1 Part 1 Endpoint

The primary endpoint will be the rate of helmet deployment during staged falls.

8.1.1 Part 2 Endpoints

8.1.1.1 Primary Study Endpoints

• Differences in Rivermead Post Concussive Scale, Seizure Questionnaire, injury-related medical records, and qualitative subject report between subjects wearing helmets during a seizure, and subjects not wearing helmets during a seizure.

8.1.1.2 Secondary Study Endpoints

- Rates of helmet deployment (per event) during seizures associated with falls, and rates of helmet deployment (per day of use) not associated with seizure.
- Qualitative description of any adverse events.

• Differences in Rivermead Post Concussive Scale, Seizure Questionnaire, injury-related medical records, and qualitative subject report between subjects following a seizure in which the helmet deployed, and seizures in which the helmet was either not being worn or did not deploy

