Short Title	Inflatable Helmet for Seizures
IRB Number	824620
Methodology	Open Label Pilot Study
Study Duration	1 year
Study Center(s)	Single Center: University of Pennsylvania
	Part 1:
	To determine reliability in helmet deployment, as evidenced by
	deployment of the helmet during 4 staged falls with normal controls or dummies
	Part 2:
	Primary:
	• To compare rates and types of head injuries and post concussive
	symptoms in seizures resulting in falls occurring while the helmet was
	worn versus seizures resulting in falls occurring while the helmet was
Objectives	not being worn.
	Secondary:
	To determine helmet deployment in seizures versus helmet
	deployment in non-seizure situations.
	To understand adverse events associated with helmet deployment
	during seizures and otherwise.
	To compare rates and types of head injuries and post concussive
	symptoms from seizures leading to helmet deployment versus
	seizures in which the helmet did not deploy. This is contingent on
	there being episodes of helmet non-deployment.
Number of Subjects	Part 1: 4 Part 2: 20
Main Inclusion and	Part 1: Healthy controls
Exclusion Criteria	Part 2: Subjects who experience at least one seizure every 6 months who do not wear static solid helmets.
Investigational Product	Hövding Inflatable Helmet

Duration of administration (if applicable)	Part 1: 1 day Part 2: 6 months
Reference therapy	Static solid helmet
Statistical Methodology	Part 1: the number of times that the helmet deploys in normal controls falling from standing.Part 2: We will compare the rates of injury and post concussive symptoms in patients wearing a helmet during a seizure leading to a fall (independent of whether or not the helmet deployed), compared to patients not wearing a helmet during a seizure leading to a fall. We will also collect the number of days that subjects assigned to wear the helmet wore the helmet.
Safety Evaluations	Medical Record Review, Rivermead Post Concussive Scale, Qualitative Subject Report
Data and Safety Monitoring Plan	The Sponsor-Principal Investigator will conduct a self-assessment to review and evaluate study data and activities. The details of monitoring are included in the Data and Safety Monitoring Plan.

BACKGROUND AND STUDY RATIONALE

This study will be conducted in full accordance all applicable University of Pennsylvania Research Policies and Procedures and all applicable Federal and state laws and regulations.

1 Introduction

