8.3 Statistical Methods

Part 2:

- Will compare rates of injury and post concussive syndrome in falls where the helmet was being worn versus falls where the helmet was not being worn.
- Descriptive statistics will be collected on the proportion of days that subjects assigned to wear the helmet actually wear the helmet
- Descriptive statistics will also be collected on rates of helmet deployment (per event) during seizures associated with falls, and rates of helmet deployment (per day of use) not associated with seizure
- Will compare rates of injury and post concussive syndrome in falls where the helmet was being worn and deployed versus falls where the helmet was either not being worn or did not deploy

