8.3.3 Safety Analysis

All subjects entered into the study and randomized at the baseline visit will have detailed information collected on adverse device effects (ADE) for the overall study safety analysis.

8.3.3.1 Part 2

• N/A

8.3.3.2 Part 2

• Compare the rates of injury and post concussive syndromes in subjects where the helmet inflated during a seizure related fall to seizure related falls where the helmet did not inflate.

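### The plan carries two comparators for one secondary objective: non-deployment alone in the Study Summary, and non-deployment pooled with not-worn falls in the endpoint and Section 8.3

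*Combined protocol and SAP*

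**What the plan says.** The Study Summary (Objectives, Secondary, third item) concerns head injuries and post-concussive "symptoms from seizures leading to helmet deployment versus" a comparator given as "seizures in which the helmet did not deploy. This is contingent on", and the condition ends with "there being episodes of helmet non-deployment".

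The endpoint for that objective, in identical words in 3.2.2.2 and 8.1.1.2, sets seizures with deployment against "seizures in which the helmet was either not being worn or did not deploy". The last bullet of 8.3 applies the same pooling to falls: "being worn and deployed versus falls where the helmet was either not being worn or did not deploy". The condition appears in none of these three places.

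Three other passages name non-deployment only and do not mention falls without a helmet:

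- 5.2 will compare circumstances, injuries and scale scores according to whether the helmet deployed.
- 8.3.2.2 will compare seizures that set the helmet off with those that do not.
- 8.3.3.2 will compare subjects where the "helmet inflated during a seizure related fall to seizure related falls where the helmet did not inflate".

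None of the three says whether the helmet must have been worn.

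The first bullet of 8.3 holds the primary contrast, worn versus not worn. The design in 3.1 is a two-period crossover in which each subject is meant to have a helmet period and a no-helmet period.

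**The concern.** The condition in the Study Summary makes sense only if falls without a helmet do not count as non-deployment. The crossover produces not-worn falls by design, so a comparator that includes them would need no such condition. The objective therefore implies a worn helmet that did not fire, although it does not use the word worn.

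The endpoint and the last bullet of 8.3 admit not-worn falls to the control. Their comparison can then be made even when no worn helmet failed to deploy, which is the situation in which the objective says it cannot be addressed. Two analysts following different sections could report different control groups for the same objective, and the choice could be made after the data are seen.

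At stake is a question of its own for the larger study: how wearers fare when the airbag does not fire. Section 12.1.2 lists non-deployment during a seizure as a foreseeable risk, and Section 2 gives estimating the effect size as one purpose of the pilot.

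**Working it through.** The plan states no figure to reproduce. Section 8.2 reads N/A, and no deployment, wear or injury rate in seizures is given. What can be checked is the make-up of the pooled control under stated assumptions.

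**Inputs from the documents**

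- About 20 subjects, with at least 5 evaluable seizures during helmet wear sought (4.5.2).
- A period ends at a helmet deployment or a seizure-related fall (5.2), so about one fall per period.
- Part 2 goes ahead if 3 of 4 staged falls deploy (3.1.1.2). The resulting 75% is used only as a reference value; it is not a rate in seizures.

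**Assumptions**

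- Falls are the unit, as in 8.3, with equal numbers in the two periods.
- w is the share of helmet-period falls with the helmet on.
- d is the probability of deployment when worn.

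**Share of not-worn falls in the pooled control.** With 20 falls per period:

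- Not worn: 20 + 20(1 − w)
- Worn, not deployed: 20w(1 − d)
- Not-worn share: (2 − w)/(2 − wd)

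| Deployment d | Full wear, w = 1 | w = 0.8 |
|---|---|---|
| 0.50 | 20/(20 + 10) = 67% | 24/(24 + 8) = 75% |
| 0.75 | 20/(20 + 5) = 80% | 24/(24 + 4) = 86% |
| 0.90 | 20/(20 + 2) = 91% | 24/(24 + 1.6) = 94% |
| 1.00 | 20/20 = 100% | 24/24 = 100% |

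With equal falls per period the share is never below 50%, and it equals 50% only at w = 1 and d = 0. At d = 0.75, worn falls would have to be at least 1/(1 − 0.75) = 4 times the not-worn falls before not-worn falls stopped being the majority. Deployments outside seizures also end a helmet period (3.1). They remove worn falls and push the share up.

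**When every worn helmet deploys.** The worn-and-deployed group is then all worn falls, and the pooled control is all not-worn falls. The last bullet of 8.3 becomes the same comparison as the first.

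**Size of the control implied by the objective.** With 5 worn falls:

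- Expected non-deployments are 5(1 − d): 5 × 0.25 = 1.25 at d = 0.75, and 5 × 0.10 = 0.5 at d = 0.90.
- The chance of none is d⁵: 0.75⁵ = 24% and 0.90⁵ = 59%.

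In those cases the Study Summary's condition would rule the comparison out, while the pooled wording would still return one.

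**The case against.** The strongest reply is that the narrower contrast is not lost. Sections 5.2, 8.3.2.2 and 8.3.3.2 all keep wording close to the objective, and the objective does not state the wear requirement either; it is inferred from the condition. The pooled wording is open about what it contains. It appears in three places and may be a deliberate contrast between falls with airbag protection and all others. The Seizure Questionnaire (7.6) records wear and deployment separately, so the categories can be split without new data. The study is a pilot with no stated hypothesis test, only one secondary comparison is affected, and the corrected control may be empty.

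All of this stands, and it limits the point. It does not remove it, because nothing in the plan says which comparator answers the objective, and the endpoint itself carries the pooled one.

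A reader might infer that the whole analysis plan adds not-worn falls, or that the study could learn nothing about non-deployment. The three narrower passages and the questionnaire do not support that. A reader might also pair 5 worn falls with 20 not-worn falls and quote 20/21.25 = 94% at 75% deployment. That joins the minimum of one count to the maximum of the other and is an extreme case for a crossover.

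The objective is readable here only in the Study Summary. Section 2.2.2 has no text in the available copy, which may be an extraction loss and is not counted against the plan.

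**Conclusion.** The point holds as an inconsistency between sections: one secondary objective, two comparators, and a condition that is missing from the endpoint and from 8.3. Under one fall per period and full wear, not-worn falls are about 67%, 80% and 91% of the pooled control at 50%, 75% and 90% deployment. At 100% deployment the contrast repeats the primary one. That they are the majority is a result of these assumptions, not a figure in the documents; it would fail only if worn falls far outnumbered not-worn falls.

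A reader might go further and infer that the secondary estimate is biased by a definite number of points. The documents do not support that. They give no injury risk for either kind of control fall, and if the two risks are equal the pooling shifts nothing. Nor is there a consequence for type I error or power, since the plan states no test and no power calculation. The effect is on what the secondary result can be taken to mean and on its use in planning the larger study. The correction should be made, but no primary result depends on it.

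**What to change.** - In 3.2.2.2, 8.1.1.2 and the last bullet of 8.3, define the comparison for this objective as worn-and-deployed versus worn-and-not-deployed.
- Restore the Study Summary's condition in the same places. If there is no worn non-deployment, state that the objective cannot be assessed.
- Add the requirement that the helmet was worn to 5.2, 8.3.2.2 and 8.3.3.2.
- Report counts and injuries for all three fall categories: worn and deployed, worn and not deployed, not worn.
- If deployed versus all other falls is still wanted, keep it as a separate comparison, labelled as such.

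The cost is wording in six places and no new data collection. The downside is a control of about one fall at the five-worn-fall target and 75% deployment, or none at all, so the result can only be descriptive. The condition in the objective already allows for an empty control.

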8.2 Sample Size and Power Determination

N/A

8.3 Statistical Methods

Part 2:

- Will compare rates of injury and post concussive syndrome in falls where the helmet was being worn versus falls where the helmet was not being worn.
- Descriptive statistics will be collected on the proportion of days that subjects assigned to wear the helmet actually wear the helmet
- Descriptive statistics will also be collected on rates of helmet deployment (per event) during seizures associated with falls, and rates of helmet deployment (per day of use) not associated with seizure
- Will compare rates of injury and post concussive syndrome in falls where the helmet was being worn and deployed versus falls where the helmet was either not being worn or did not deploy

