2.2 Part 2 Objectives

2.2.1 Primary Objective

• To compare rates and types of head injuries and post concussive symptoms in seizures resulting in falls occurring while the helmet was worn versus seizures resulting in falls occurring while the helmet was not being worn

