3.1.2.2 Study Intervention Phase

- Subjects assigned to wear the helmet will be asked to wear the Hövding Helmet during their daily lives with the following exceptions: swimming, bathing, driving or riding in a car, participating in activities with frequent changes in velocity such as sports, or handling children or infants.
- All 20 Subjects will complete a Seizure Calendar that will detail which how often and what type of seizures they are having
- During the time they are assigned to the helmet group, subjects will also record the number days that they wear the helmet.
- All 20 Subjects will complete a Seizure Questionnaire, which will be self-administered after the subject has a seizure to detail the circumstances of the seizure and any injuries sustained.
- During the time they are assigned to the helmet group, subjects helmet will complete a Helmet Deployment Questionnaire, which will be self-administered after the Helmet deploys to detail the circumstances of its deployment
- Those subjects able to do so will complete a Rivermead Post concussive scale which will be selfadministered 48 hours after their seizure if they sustain a head injury during a seizure or if the helmet deploys during a seizure, regardless of head injury.
- The study team will make monthly contact with each subject, to ask about seizure frequency, helmet deployment, and any other relevant information.
- If any subject seeks medical care for injuries during the trial, the study team will make every effort to obtain related medical records.
- Subjects will be instructed to contact the study team after they experience a seizure that results in a fall, or after a helmet has been deployed to schedule a follow-up visit.

3.1.2.3 Visit 2

After a helmet has been deployed or the subject experiences a seizure that results in a fall, subjects will be asked to return for visit 2. At this visit, the following study procedures will be performed:

- Medical History review
- Adverse Device Events review
- Helmet collection, if applicable
- If a subject with a VNS experiences a helmet deployment, their VNS will be interrogated at visit 2. If a problem is detected, appropriate clinical care will be provided.
- Dispense Helmet, if applicable
- Collect Seizure Calendar
- Collect Seizure Questionnaire
- Collect Helmet Deployment Questionnaire (if subject was assigned to wear a helmet at visit 1)
- Collect Rivermead Post Concussive Scale (for patients able to complete)
- Dispense Seizure Calendar

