3.2.2 Part 2 Endpoints

3.2.2.1 Primary Study Endpoints

• Differences in Rivermead Post Concussive Scale, Seizure Questionnaire, injury-related medical records, and qualitative subject report between subjects wearing helmets during a seizure, and subjects not wearing helmets during a seizure.

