8.3.2 Efficacy Analysis

8.3.2.1 Part 1

• Number of times the helmet deploys in normal controls (or dummies) falling from a standing position.

8.3.2.2 Part 2

- Number of days that subjects in the helmet group actually wore the helmet
- Compare the fraction of the time the device deployed during a seizure that resulted in a fall
- Compare the number of times the helmet deployed in a seizure vs. non-seizure event
- Compare seizures that trigger helmet deployment to those that do not trigger helmet deployment

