8.4 Subject Population(s) for Analysis

• All-randomized population: Any subjects in the study, regardless of whether they were assigned to wear the helmet, will be used for any analysis comparing helmet wear vs. no helmet wear.

9 Adverse Device Effects and Adverse Events

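### Part 2 plans no injury comparison by randomised period, and its as-worn comparison puts falls in helmet-off activities only in the not-worn set: a small gap that section 8.3 can close cheaply

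*Combined protocol and SAP*

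**What the plan says.** Section 3.1 describes Part 2 as a randomised two-way crossover in which block randomisation decides whether the helmet or the no-helmet period comes first. Under sections 3.1 and 5.2, a period ends at a seizure with a fall or at a helmet deployment.

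The planned outcome comparisons do not use that assignment:

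- **By wear.** The primary objective (2.2.1) concerns "seizures resulting in falls occurring while the helmet was worn versus seizures resulting in falls occurring while the helmet was not being worn". The primary endpoints (3.2.2.1, repeated in 8.1.1.1) are differences "between subjects wearing helmets during a seizure, and subjects not wearing helmets during a seizure". Section 8.3 contrasts "rates of injury and post concussive syndrome in falls where the helmet was being worn versus falls where the helmet was not being worn". The Study Summary also groups by wear, whether or not the helmet deployed.
- **By deployment.** Section 8.3.2.2 says "Compare seizures that trigger helmet deployment to those that do not trigger helmet deployment". The safety analysis in 8.3.3.2 compares "subjects where the helmet inflated during a seizure related fall to seizure related falls where the helmet did not inflate". Sections 3.2.2.2, 8.1.1.2 and 8.3 also set worn-and-deployed falls against all others.

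Assignment appears in the methods only to describe days of wear (8.3, 8.3.2.2). Section 8.4 includes all randomised subjects, "regardless of whether they were assigned to wear the helmet, will be used for any analysis comparing helmet wear vs. no helmet wear". That settles who is analysed, but the contrast is still wear against no wear.

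Section 3.1.2.2 asks helmet-period subjects to wear the device in daily life "with the following exceptions: swimming, bathing, driving or riding in a car, participating in activities with frequent changes in velocity such as sports". The same sentence adds care of children or infants.

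**The concern.** A subject who follows section 3.1.2.2 has the helmet off in the listed activities in both periods. A fall there can never be a worn fall, so the not-worn set contains such falls and the worn set contains none. Helmet-period falls in which the subject chose not to wear the device go the same way. If injury risk per fall differs between those falls and the rest, the as-worn ratio differs from 1 even for a helmet that does nothing. The documents give no injury risk by activity, so they do not fix the direction.

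The pilot is meant to estimate effect size for a larger study (sections 1 and 2). Section 8.3 has no restriction by activity and no by-period or within-subject result. It reports the proportion of days with wear, which does not show whether the helmet was on at the moment of a fall.

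**Working it through.** The plan has no figure to reproduce: section 8.2 is marked not applicable. From the documents come the randomised order (3.1), the helmet-off list (3.1.2.2), and the target of at least 5 evaluable seizures during wear among about 20 subjects (4.5.2). **Every other input below is an assumption.**

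**Notation.** Falls are equally frequent in the two periods. s is the share of falls in listed activities, where the helmet is never worn. v is the probability of wear in other helmet-period falls. qe and qo are the unprotected injury risks in listed and other falls. R is the true ratio when worn.

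- Worn risk = R × qo
- Not-worn risk = [s·qe + (1−s)(1−v)·qo + s·qe + (1−s)·qo] / [s + (1−s)(1−v) + 1]
- By-period ratio = [s·qe + (1−s)(v·R·qo + (1−v)·qo)] / [s·qe + (1−s)·qo]

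**Inert helmet (R = 1), v = 0.8, qo = 0.40.** At s = 0.05 and qe = 0.60, the not-worn risk is (0.030 + 0.076 + 0.030 + 0.380) / 1.24 = 0.416, and the as-worn ratio is 0.40 / 0.416 = 0.96. At qe = 0.20 it is 0.40 / (0.476 / 1.24) = 1.04.

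| s | as-worn, qe = 0.60 | as-worn, qe = 0.20 | by period |
|---|---|---|---|
| 0.05 | 0.96 | 1.04 | 1.00 |
| 0.10 | 0.93 | 1.08 | 1.00 |
| 0.25 | 0.85 | 1.22 | 1.00 |

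If qe = qo, the as-worn ratio is 1.00 at every s.

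**Make-up of the sets, per 100 falls per period.** At s = 0.05, 76 falls are worn and 5 + 19 + 5 + 95 = 124 are not worn. Of the not-worn falls 10 (8%) are in listed activities; of the worn falls, none. At s = 0.25 there are 60 worn falls, and 50 of the 140 not-worn falls (36%) are in listed activities.

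**Restriction in both periods.** Dropping falls in listed activities gives qo / qo = 1.00 for an inert helmet, provided voluntary non-wear is unrelated to risk. The not-worn set falls from 124 to 114 (s = 0.05) or from 140 to 90 (s = 0.25).

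**What the restriction leaves.** Take s = 0, with half of falls at risk 0.6 and half at 0.3. If the helmet is worn in 50% of the former and 90% of the latter, an inert helmet gives (0.285 / 0.70) / (0.615 / 1.30) = 0.407 / 0.473 = 0.86. With the wear rates reversed it gives 0.493 / 0.427 = 1.15. By assigned period the ratio is 1.00 in both cases.

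**What the by-period result costs.** At s = 0.05, v = 0.8 and a true R of 0.50, as-worn gives 0.48 (qe = 0.60) or 0.52 (qe = 0.20). By period gives 0.258 / 0.410 = 0.63 or 0.238 / 0.390 = 0.61. For harm with R = 1.50 and equal risks, by period gives 1 + 0.5 × 0.8 × 0.95 = 1.38 at s = 0.05, and 1.30 at s = 0.25.

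**Scale of imprecision.** With 2 of 5 worn and 6 of 15 not-worn falls injured (assumed), the ratio is 1.00. The log standard error is √(1/2 − 1/5 + 1/6 − 1/15) = √0.40 = 0.632, so the approximate 95% interval is 0.29 to 3.45.

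**The case against.** The strongest reply is that this is a small descriptive pilot and as-worn is the right in-use question. Much of that stands.

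- At a 5% share the bias is about 4%, against an interval of 0.29 to 3.45. The larger table entries need a 25% share, which nothing in the documents supports.
- Sections 2 and 3.1 aim at seizures from standing. Falls while swimming or in a car are largely outside that aim, which probably limits the problem further. Section 8.3 does not repeat that limit, so it does not remove the problem.
- When the helmet works, as-worn is nearer the truth than by-period in the example above, and by-period also dilutes harm. By-period therefore cannot replace as-worn.
- By-period is not clean either. A non-seizure deployment ends the helmet period and has no counterpart in the other period. A subject with no seizure-related fall at 3 months becomes a screen fail (3.1, 5.2). Which falls are observed can therefore differ by period.

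A reader might infer that the as-worn analysis is invalid, that it will show a false benefit, or that the bias will pass into the larger study. The documents support none of these. Wear is the stated objective, the direction is not fixed, and nothing says the larger study would reuse this comparison. Nor can one infer that activity goes unrecorded. Sections 3.1 and 3.1.2.2 have the Seizure Questionnaire cover circumstances, section 7.6 gives a non-exhaustive list, and the form itself is not shown.

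**Conclusion.** The gap is in the text: order is randomised, yet no planned Part 2 injury or post-concussive comparison is by assigned period. The as-worn comparison gives the not-worn set a type of fall that the worn set lacks, so its estimate can be biased either way.

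The size is unknown. It is about 4% under the assumed 5% share and risks of 40% against 60% or 20%, and zero if the risks are equal. Risk-related voluntary non-wear could add to it (0.86 or 1.15 in the assumed scenario). All of this is small beside the imprecision from about 5 worn falls. It is a minor point, worth acting on because the remedy is cheap and uses data largely collected already.

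**What to change.** In section 8.3, keep as-worn as the main comparison and add:

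1. A pre-specified descriptive comparison of injury by assigned period, within subject where both periods have a fall.
2. The number and proportion of helmet-period falls with the helmet on.
3. The as-worn comparison repeated with falls in the section 3.1.2.2 activities excluded from both periods, noting that this does not remove risk-related voluntary non-wear.
4. A statement that the by-period result is diluted by non-wear for both benefit and harm, is conditional on having a fall, and is affected by the helmet period also ending at a non-seizure deployment and by the 3-month screen-fail rule. It is therefore not fully protected by randomisation.

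Confirm that the Seizure Questionnaire captures activity at the time of the fall. The Helmet Deployment Questionnaire (7.7) does so, but only for deployments.

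The cost is a few lines and possibly one questionnaire item. Objectives, endpoints, wearing instructions, sample size and visits do not change. The downside is fewer not-worn falls in the restricted set and a diluted by-period result, so the results must be read together.
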